Other parent artery flow diverter devices are in clinical use, including FRED, LVIS (MicroVention Terumo), Surpass (Stryker), Silk (Balt), p64 (PhenoX), Derivo (Acandis), and BRAVO (Cerenovus). All devices are made from metallic meshes similar to Neqstent. The published literature on these devices is less extensive compared to Pipeline Embolization Device but shows similar findings.

 Cerus Endovascular	Document Number DNQS428-01	Rev. F	Page 21 of 119
Clinical Investigation Plan	Title		
Confidential & Proprietary	Coil Assisted Flow Diversion: A prospective, single arm, multi-center study to assess the safety and performance of Neqstent in adjunctive therapy (CAFI Study)		

The published literature is very clear that flow diverters such as Pipeline Embolization Device, are now playing an increasing role in the treatment of wide-neck, large and giant, complex IAs. Their use in smaller IAs has been explored but is not accepted as standard treatment.

WEB (Woven Endobridge, Sequent Medical, Terumo, Aliso Viejo, California) is an intrasaccular flow diverter that shares characteristics with Neqstent and has both CE Mark and FDA approval. Because of the similarities, the published literature on WEB use is highly relevant.

- Ding reported use of WEB in an animal study similar to those done to support Neqstent. The study showed complete occlusion in 33% of cases.
- Behme reported a retrospective assessment of use of WEB in 52 patients (55 IAs), including 15 ruptured IAs. The device was deployed in all patients and implanted in 93%. Procedure complications occurred in 12%, including 2 thromboembolic events, 2 thrombus formations, 1 high-grade posterior cerebral artery stenosis, and 1 aneurysm rupture. None of these had clinical sequelae. Favorable angiographic results were seen in 29 (53%).
- Pierot reported use of WEB in 21 IAs at 3 centers in the EU. All IAs were treated with the device and adjunctive treatment (coiling and/or stent placement) was used in 24% of patients. One patient (4.8%) has a symptomatic thrombotic event. Inadvertent detachment of WEB occurred in 1 patient. Complete occlusion of the target IA was seen in 7 (33%) IAs.
- Colla reported use of WEB in 4 wide-necked basilar tip bifurcation IAs at a single Italian hospital. There were no perioperative adverse events and satisfactory occlusion was seen in all cases.

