- Wallner reported a patient treated with WEB who had IA recurrence requiring retreatment.
- Pierot reported a prospective multicenter French study of use of WEB in 62 patients (63 IAs). Two versions of WEB were used. Morbidity was low (3.2% overall). Angiographic occlusion was not reported.
- Lubicz reported a multicenter experience with WEB use in 45 patients with 45 IAs treated with WEB. Good clinical outcome was observed in 93%. Complete occlusion was observed in 30 (67%) patients in the short term (median 6 months) and 26 patients (58%) in the long term (median 13 months).
- Cognard reported experience with WEB in 15 patients (15 IAs). Worsening of IA occlusion status was seen in 10 (67%) of cases, with compression of the implant. Complete occlusion at last follow-up was seen in only 1 case (6.7% of all patients).
- Papagiannaki reported multicenter French retrospective WEB use to treat 83 patients with 85 IAs. Periprocedural complications were seen in 10.8%, with permanent neurologic deficits in 3.9%. Complete IA occlusion was seen in 37 (44%) of IAs at a median of 5.3 months of follow-up.
- Fiorella reported interobserver agreement when judging IA occlusion with use of WEB. The degree of agreement was high.

 Cerus Endovascular	Document Number DNQS428-01	Rev. F	Page 22 of 119
Clinical Investigation Plan	Title		
Confidential & Proprietary	Coil Assisted Flow Diversion: A prospective, single arm, multi-center study to assess the safety and performance of Neqstent in adjunctive therapy (CAFI Study)		

The published literature on WEB is promising: it shows that intrasaccular flow diverters can be useful in a subset of IAs (primarily wide-necked IAs at arterial bifurcations). Periprocedural safety was good; complete occlusion of the target IA was often observed. However, compaction of the device may limit overall success rates.

In addition, there are also braided and laser-cut intra-arterial dwelling stents, such as, Solitaire AB (Medtronic), Enterprise 2, PulseRider (Cerenovus), LVIS Jr (Microvention Terumo), Baby LEO (Balt), ATLAS, Neuroform (Stryker), ACCLINO Flex Plus (Acandis) and pCONUS (PhenoX). Substantial literature exists to support these various braided and laser-cut intra-arterial dwelling stents. Please see literature samples in **Table 4**.

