
 
Cerus Endovascular
	
Document Number DNQS428-01
	
Rev. F
	
Page 33 of 119

Clinical Investigation Plan
	
Title
		

Confidential & Proprietary
	
Coil Assisted Flow Diversion: A prospective, single arm, multi-center study to assess the safety and performance of Neqstent in adjunctive therapy (CAFI Study)
		

All patients must sign a study-specific consent form prior to the commencement of any protocol-specific assessments and/or procedures. Final qualification will occur during the implant procedure due to the need for confirmation of IA appropriateness with cerebral angiography.

The patient is enrolled at the time of consent and is considered a study subject in the reporting analysis group only when the patient is fully qualified and at least one Neqstent device has been placed into the patient's body. The following listing provides examples of patient enrollment scenarios for the study:

- The patient is not considered enrolled but not included in the primary analysis group in the study: if at the onset of the procedure in the initial DSA, the investigator determined the patient's IA was not suitable for treatment with the device, thus, no attempt was made by the investigator to place the device. The patient will be treated outside of the study per the investigator's usual practices. The reason for not treating the patient must be documented on a study exit form. The patient is not included in the primary analysis group because the Neqstent was never opened or deployed inside the patient. All patients will be listed in the final report.
- The patient is considered enrolled but not included in the primary analysis group in the study: at the onset of the procedure, the investigator determined the subject's IA was suitable for treatment with the device. The investigator attempted but was unable to place the device within the IA and the subject required alternative treatment. The subject is considered enrolled for the purposes of the study but will only be followed through the 1-month visit. All failed implant attempts will be reported in the final report.

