## 10.6 Sample Size Rationale and Statistical Considerations

This is a single arm study designed to provide adequate data for the purpose of a pre-market study. It is expected the 51 patients with evaluable data at 6 month and 12 month follow-up (where necessary) will show adequate evidence of safety and performance of Neqstent device.

For the purpose of sample size calculation, the primary outcome measurement is assumed to be the composite of the listed primary endpoint components.

Extensive literature search was conducted to gather information on the non-inferiority margin. Due to limited results found in literature, the non-inferiority margin for this study,  $\delta = 10\%$ , was chosen to align with the study design.

The sample size estimation was based on the following assumption:

- Success rate of the investigational is expected to be 70%
- Success rate of standard treatment is estimated to be 55%
- Power is set at 80% and one-sided significance level is set at 5%
- Expected rate of attrition is 10%

Based on the assumptions, a total of 46 subjects are required to show that the expected success rate of 70% is different than the true rate of 55% with a delta of 10%. Adding in additional subjects for anticipated loss to follow-up, 51 subjects are needed to be enrolled for a total of 46 subjects with 6 month data.

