### Analysis Population

The safety population consists of all patients who are implanted with the study device. The primary analysis for all safety endpoints will be performed on this population.

The analysis for all primary and secondary study endpoints and baseline, procedural and follow-up characteristics will be performed on an intent-to-treat analysis population which will include all available data for all enrolled subjects. Standard summary statistics will be calculated for all study variables.

 Cerus Endovascular	Document Number DNQS428-01	Rev. F	Page 46 of 119
Clinical Investigation Plan	Title		
Confidential & Proprietary	Coil Assisted Flow Diversion: A prospective, single arm, multi-center study to assess the safety and performance of Neqstent in adjunctive therapy (CAFI Study)		

The primary safety endpoint will be calculated as the proportion of subjects with death of any nonaccidental cause or any major stroke within the first 30 days after treatment or major stroke or death due to neurological cause from day 31 to 6 months after treatment.

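### Subjects with a failed Neqstent placement drop out of the 6-month occlusion rate under either stated population, so the rate describes implanted subjects only

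*Combined protocol and SAP*

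**What the plan says.** Three parts of the plan bear on who is counted in the primary performance rate.

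- **Enrollment scenarios (synopsis and 7.5).** A patient joins the reporting analysis group "only when the patient is fully qualified and at least one Neqstent device has been placed into the patient's body" (7.5 wording). One scenario is a suitable aneurysm where "The investigator attempted but was unable to place the device within the IA and the subject required alternative treatment". Of this subject the plan says "The patient is considered enrolled but not included in the primary analysis group in the study: at the onset of the procedure", and adds that the subject "will only be followed through the 1-month visit". Failed attempts are to be reported in the final report. A subject who was implanted and then needed another endovascular device stays in the primary group.
- **Populations (10.2 and 10.6).** Section 10.2 puts all patients in the ITT set and evaluates endpoints in both ITT and per-protocol sets. Section 10.6, Analysis Population, analyses all primary and secondary endpoints on an ITT set "which will include all available data for all enrolled subjects". Endpoint Analysis in 10.6 then rules out imputation of missing data.
- **Benchmark (10.6).** "Success rate of standard treatment is estimated to be 55" percent, against 70% expected for Neqstent, with a 10-point margin, 80% power and a one-sided 5% level. No source or denominator is given for the 55%. Section 10 also says the study is not powered for statistical significance, and 10.1 calls it descriptive.

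**The concern.** Failure to place the device is the most direct failure of performance, and its outcome is known on the day of the procedure. This is not the problem of subjects who miss the 6-month angiogram. If failed attempts leave the denominator, the headline answers how often an aneurysm is occluded once Neqstent is in. A reader will take it as how often treatment with Neqstent works. The two questions differ by the failed-placement rate, and the difference always favours the device.

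The plan also contradicts itself on which population is primary, so two analysts could follow it in good faith and report different denominators. If the rate is then set beside 55%, the comparison is fair only if both figures count failed placements in the same way.

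**Working it through.** **1. The plan's own sample size.** Inputs from 10.6: 55%, 70%, margin 10 points, one-sided 5%, power 80%.

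n = (1.645 + 0.842)² × (0.55×0.45 + 0.70×0.30) / (0.70 − 0.55 + 0.10)² = 6.183 × 0.4575 / 0.0625 = 45.3, rounded up to 46. With 10% added, 46 × 1.10 = 50.6, rounded up to 51.

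The plan's 46 and 51 reproduce. The formula is the per-arm size of a two-arm non-inferiority comparison, so in a single arm the null could be read as 45% (55% less the margin) or as 55%. Both are carried below.

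**2. Following one failed attempt through the plan.**

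- By 7.5 and the synopsis, the subject is outside the primary analysis group.
- By 10.2 and 10.6, the subject is in the ITT set. Follow-up stops at 1 month (or when related adverse events resolve, by the synopsis and 11.5), so no 6-month angiogram is scheduled and there is no Raymond Roy grade.
- The ITT analysis uses available data, 10.6 does not impute, and no sentence scores a failed placement as non-success.

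The subject is absent from the Grade 1 rate by either route.

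**3. Size of the overstatement.** Let f be the share of attempts that fail, each counted as non-success. Then per-attempt rate = implanted-only rate × (1 − f). The documents give no failed-placement rate for Neqstent. The one such figure is in section 4, for a WEB series: "The device was deployed in all patients and implanted in 93" percent, so f = 7% is borrowed as an assumption and varied. An implanted-only rate of 70% becomes:

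| f | per-attempt rate |
|---|---|
| 2% | 68.6% |
| 5% | 66.5% |
| 7% | 65.1% |
| 10% | 63.0% |

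This step needs no hypothesis test and no benchmark.

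**4. Effect on a comparison with 55%, if that figure is per treated aneurysm.** Assumptions: 46 evaluable implanted subjects; an exact one-sided binomial test at 5%, which the plan does not state; a true per-attempt rate p0 equal to the null. The rate seen among implanted subjects is p0/(1 − f).

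- Null 45%: the smallest passing count is 27 of 46, attained size 4.3%. At f = 7%, 0.45/0.93 = 48.4%, and P(X ≥ 27) = 10.5%.
- Null 55%: the smallest passing count is 32 of 46, attained size 3.2%. At f = 7%, 0.55/0.93 = 59.1%, and P(X ≥ 32) = 9.7%.

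| f | pass, null 45% | pass, null 55% |
|---|---|---|
| 2% | 5.6% | 4.4% |
| 5% | 8.2% | 7.1% |
| 7% | 10.5% | 9.7% |
| 10% | 15.1% | 15.3% |

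**5. What the background series show about denominators.** In the series with 93% implanted, the 53% favorable result is 29/55 = 52.7%, so unimplanted cases stayed in; over the implanted share it would be 29/(0.93 × 55) = 56.7%. For a second series the plan reports "Complete IA occlusion was seen in 37 (44%) of IAs at a median of 5.3 months of follow-up", which is 37/85 = 43.5%. A third is 30/45 = 66.7%. The last two divide by all aneurysms described as treated, but no failed placements are reported for them.

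**The case against.** A reader might infer that the plan's own comparator rates count every treated aneurysm, and hence that a device at the benchmark would pass 2.4 to 3 times as often as it should. The documents do not support that, for four reasons.

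- **The benchmark's denominator is unknown.** The 55% is for standard treatment and is never linked to the WEB series in section 4. Only 29/55 shows unimplanted cases in the denominator. That series is retrospective, includes 15 ruptured aneurysms (excluded here) and reports favorable results rather than complete occlusion. The 37/85 and 30/45 figures fit an implanted-only denominator equally well. If the 55% is per implanted subject, this asymmetry disappears.
- **There is no pass rule.** Section 10 calls for clinical judgement, and 10.6 gives a level and margin for sizing only.
- **The multiple depends on its base and on f.** Ratios of 2.4 and 3.1 divide by attained sizes of 4.3% and 3.2%. Against the nominal 5%, 10.5% and 9.7% are about 2.1 and 1.9 times. Over f from 2% to 10%, the ratio to attained size runs from 1.3 to 4.8. Neck-only sizing, re-sheathing, committee review of images and proctoring may keep Neqstent's f low.
- **Failed placements are disclosed.** They will be listed in the final report, so a reader could rebuild the per-attempt rate.

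A reader might also infer that failed attempts are simply ruled out. Sections 10.2 and 10.6 say otherwise on paper, and the per-protocol set in 10.2 names study failures who leave for alternate treatment. Scoring a failed placement as non-success is also a choice, since alternative treatment may occlude the aneurysm.

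All of this stands against the comparator claim and a single multiple. It does not remove the defect: the populations conflict, no text scores a failed placement, and listing failures in a report does not put them in the endpoint. Calling the study descriptive does not help either, because the descriptive headline is itself the conditional rate.

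**Conclusion.** The point holds in a limited form. The plan contradicts itself on whether failed attempts belong to the primary performance population, and under either reading they drop out of the 6-month Grade 1 rate. That rate is conditional on successful implantation. It overstates per-attempt performance by 1/(1 − f), given that a failed placement counts as non-success: about 5 points at 70% with f = 7%, and 1.4 points at f = 2%.

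Bias in a comparison with 55% is conditional on that figure being per treated aneurysm. If it is, and an exact one-sided 5% test is applied to 46 subjects, a device at the benchmark passes 10.5% (null 45%) or 9.7% (null 55%) of the time at f = 7%. Over f from 2% to 10% the ranges are 5.6% to 15.1% and 4.4% to 15.3%. At 2% the effect is small, and for the 55% null the pass rate stays below the nominal 5%. The test and the value of f are assumptions of this check, not statements of the plan.

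**What to change.** - Reconcile the enrollment scenarios in the synopsis and 7.5 with the ITT definitions in 10.2 and 10.6, so that one primary performance population is stated: all subjects in whom Neqstent placement was attempted.
- In 10.6, Endpoint Analysis, score an attempted-but-unplaced subject as a performance non-success at 6 months, so that the available-data and no-imputation rules no longer remove the subject.
- Use this rate for any comparison with 55%, and state the source and denominator of the 55%.
- Report the implanted-only rate as a labelled supportive result.

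This is a change of wording. It needs no extra visits, imaging or patients, because failed attempts are already recorded and their score does not depend on an angiogram. The cost is a slightly lower headline rate, for example about 65% instead of 70% at 7% failed attempts.

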**Table 7. Neqstent Sizes**

REF (Catalog Number) – Diameter	Aneurysm Neck (mm)
NQS407 – 7 mm	3.0 - 5.0
NQS409 – 9 mm	4.0 - 6.0
NQS411 – 11 mm	5.0 - 8.0

## 7.6 Baseline Evaluation

The baseline evaluation is performed after signing the consent form and prior to the implant procedure. During the baseline evaluation, the investigator and/or coordinator will record basic medical information on the study case report form (CRF), including known diagnoses and daily medication use. Any relevant neurologic findings will be recorded on the CRF. A modified Rankin Scale (mRS) will be performed at baseline. The mRS is a widely used scale for measuring the degree of disability or dependence in the daily activities of people who have suffered a stroke or other causes of neurological disability.

All images obtained at screening or from images obtained prior to screening as standard, including the 3D angiogram, MRA and/or CTA are to be submitted for review to the patient selection committee to confirm the subject's eligibility for use of the Neqstent. The Neqstent procedure may be scheduled following confirmation from the patient selection committee. Additionally, the images obtained at baseline shall be submitted to the independent core laboratory.

### 7.6.1 Angiogram

A cerebral angiogram that includes a 3D rotational angiogram shall be performed prior to the Neqstent implant placement procedure to allow proper assessment of the target IA being treated. The angiogram will include the acquisition of a 3D rotational angiogram of the aneurysm and parent vessel. Imaging will always be performed on the day of the procedure which will be used for core laboratory baseline for comparison at 6 months and at 12 months if performed due to lack of complete occlusion at 6 months. All imaging must be submitted to the independent core lab for analysis.

 Cerus Endovascular	Document Number DNQS428-01	Rev. F	Page 35 of 119
Clinical Investigation Plan	Title		
Confidential & Proprietary	Coil Assisted Flow Diversion: A prospective, single arm, multi-center study to assess the safety and performance of Neqstent in adjunctive therapy (CAFI Study)		

## 7.7 Implant Procedure

### 7.7.1 Preoperative Preparation

The subject undergoes standard preoperative preparation. The device implant procedure must be performed under general anesthesia.

### 7.7.2 Arterial Access

Standard methods are used to gain access to the femoral artery. Standard methods are used (e.g., sheaths and guide catheters, distal support guides) to obtain access to the IA. Tri-axial approach, although not mandatory, is highly recommended.

### 7.7.3 Angiogram

A cerebral angiogram of the target IA and the parent artery at the beginning of the procedure will be performed to confirm final eligibility for the study. These images will be the baseline submitted to the independent core laboratory for future comparisons at 6 months and 12 months.

### 7.7.4 Neqstent Procedure

Neqstent placement is described in detail in the Instructions for Use (IFU). Briefly, the target IA is accessed via standard methods. A 0.027" microcatheter is placed into the target IA. The Neqstent device is introduced into the microcatheter and slowly delivered into the target IA. The device is deployed at the neck of the aneurysm after the coiling microcatheter tip is inside the aneurysm sac, which would result in the microcatheter being jailed between the aneurysm wall and the Neqstent or the Neqstent is deployed prior to the introduction of the coiling microcatheter where the operator will navigate the coiling microcatheter through the mesh of the Neqstent to gain access to the aneurysm sac.

The Neqstent remains attached to the delivery wire throughout the entire embolization procedure and detachment or the device is the final step in the procedure once the physician has embolized the aneurysm sac with coils.

A final post-placement angiogram, which includes a 3D angiogram of the aneurysm and parent vessel, will be performed and all devices are removed from the body. All relevant radiographic images should be saved. Specifically, the investigator should document flow disruption and occlusion compared to pre-placement flow. Any device deficiencies, technical complications or adverse events occurring during the procedure should be noted in the CRF.

All images captured during the procedure, including the 3D angiogram, shall be submitted to the independent core laboratory.

Pre and Peri-operative anti-platelet use is not excluded and may be used at the discretion of the operator.

## 7.8 Hospital Discharge

The subject will be discharged from the hospital as per standard practices. Prior to discharge, the investigator should evaluate the subject for any adverse events and perform a neurologic examination.

 Cerus Endovascular	Document Number DNQS428-01	Rev. F	Page 36 of 119
Clinical Investigation Plan	Title		
Confidential & Proprietary	Coil Assisted Flow Diversion: A prospective, single arm, multi-center study to assess the safety and performance of Neqstent in adjunctive therapy (CAFI Study)		

## 7.9 Follow-Up

Following discharge, the subject will have a follow-up visit at 1 month, 6 months, 12 months and 24 months after the implant procedure. At each study visit, the subject shall be assessed for any new adverse events (AEs). A standard neurologic examination should be performed to evaluate for any new adverse events. A modified Rankin Scale (mRS) will be recorded at each follow-up visit. It is expected that most target IAs will be asymptomatic and the likelihood of post-placement neurologic changes is very low. The NIH Stroke Scale assessment should be obtained within 24 hour after a stroke in the event a subject is diagnosed with a stroke. Cerebral angiography will be repeated at 6 months and 12 months (if the Raymond Roy scale is Grade 2 or higher at 6 months). The cerebral angiography will include a 3D angiogram. The investigator should ensure that follow-up angiography is done with identical views to maximize the ability to compare baseline and post-treatment views. All angiographic images should be submitted to the independent core laboratory following the image transfer protocol. The target IA status shall be evaluated by an independent core laboratory.

The study's schedule of assessments and post-treatment visit windows are shown in

